STUDY TITLE:

**“VALUE OF TEMPORARY OCCLUSION OF THE
UTERINE ARTERIES IN LAPAROSCOPY
MYOMECTOMY”**

INVESTIGATOR: [name] [name]. Head of the Gynecology Section.
Ramon y Cajal Hospital in Madrid.

CENTER: RAMÓN Y CAJAL UNIVERSITY HOSPITAL

Address: [name].

Gynecology Service

Email: [contact]

[contact]

SUMMARY:

1. Objectives:

- Main objective: To analyze the patients who underwent a laparoscopic myomectomy, to assess whether there are significant differences in terms of a decrease in intraoperative blood loss between patients with temporary clamping of the uterine arteries and utero-ovarian ligaments and patients without temporary occlusion during the surgical technique.

- Secondary objectives: To determine the surgical time of each technique, the improvement of the symptoms for which the patient is operated, the length of hospital stay and the possible complications of each technique.

2. Methods:

- **Study design** : This is a randomized prospective longitudinal clinical trial in patients with fibroids who require surgery, from the Gynecology service of the Ramón y Cajal Hospital.

- **Study population and total number of subjects** :

A total of 37 patients who underwent laparoscopic myomectomy with temporary occlusion of the uterine arteries and utero-ovarian ligaments using clips will be analyzed with a control group of 37 patients who underwent laparoscopic myomectomy with the traditional technique (surgery without temporary occlusion of uterine arteries).

The sample size has been calculated based on data published in the literature, where there is a difference in hemoglobin levels of 0.7 g/dl between the two groups, with a statistical power of 80% and an alpha error of 5%.

1. INTRODUCTION.

Uterine fibroids are the most frequent benign tumors originating in smooth muscles of the female genital tract.

Fibroids appear in 70% of middle-aged women. They are often the cause of abnormal uterine bleeding, pelvic pain and pressure, urinary and intestinal symptoms, and/or pregnancy complications. However, many fibroids are small and asymptomatic. About 25% of white women and 50% of black women will develop symptomatic fibroids. Fibroids are more common among women who are overweight or obese. Potentially protective factors for the appearance of fibroids are pregnancy and smoking, in women who consume more than 10 cigarettes per day, except in black women, and although the mechanism by which the incidence decreases is not clear, a causal relationship does seem to exist.

Treatment of women with uterine leiomyomas should be individualized based on symptomatology, size and location of the leiomyoma, age, patient need and desire to preserve fertility or the uterus, availability of therapy, and surgeon experience.

Although hysterectomy is the definitive surgical treatment of symptomatic fibroids in women who do not wish to preserve fertility or their uterus, myomectomy is the treatment of choice in patients with an unfulfilled reproductive desire or express desire to maintain their uterus and who are not candidates for medical treatment.

Surgical planning for myomectomy should be based on the location, size, and number of fibroids with the aid of appropriate imaging tests, such as high-resolution ultrasonography or magnetic resonance imaging (MRI).

Intraoperative bleeding is one of the most frequent complications of laparoscopic myomectomy and may even require the need for transfusion on many occasions. For this reason, methods have been proposed that could reduce bleeding during surgery, such as temporary occlusion of the uterine arteries and utero-ovarian ligaments. The efficacy and safety of this technique for its application during laparoscopic myomectomy has not yet been clearly investigated.

2. GOALS

Main objective :

- To identify the efficacy of temporary occlusion of the uterine arteries during laparoscopic myomectomy by comparing blood loss (by assessing pre- and postoperative hemoglobin in g/dL and intraoperative blood aspirate in milliliters), in 2 groups of patients with symptomatic fibroids undergoing laparoscopic surgery, one with temporary occlusion of uterine arteries and uteroovarian ligaments and one without such occlusion.

Secondary objectives:

- Compare the surgical time of each technique.
- Compare the need for transfusion between both groups.
- Compare the improvement of the symptoms for which the patient is operated.
- Compare the length of hospital stay in each group
- Compare possible complications of each technique.

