3. METHODOLOGY

3.1. DESIGN : Longitudinal prospective randomized clinical trial.

3.2. SUBJECTS OF STUDY : Patients with symptomatic fibroids who require surgery to treat them, from the Gynecology Service of the Ramón y Cajal Hospital. Patients will be randomized into 2 groups: exposed (patients with temporary occlusion of the uterine arteries by clips during surgery) and non-exposed (patients without temporary occlusion of the uterine arteries during surgery).

A patient will be recruited in the pre-surgical consultation when laparoscopic myomectomy is indicated, randomizing both groups by simple random sampling. An informed consent will be delivered to the patients, who have to accept and sign in order to participate in the study. The diagnosis of the presence of fibroids will be made by abdominal and/or transvaginal gynecological ultrasound and/or nuclear magnetic resonance. Fibroids will be quantified, measured and their location described.

3.3. INCLUSION CRITERIA : The inclusion criteria to participate in the study are the existence of uterine fibroids with an indication for laparoscopic surgery and the patient's desire to preserve the uterus.

3.4. EXCLUSION CRITERIA : Patients who do not meet the inclusion criteria, women with symptomatic fibroids who are not candidates for laparoscopic surgery and/or do not

wish to preserve the uterus, those patients who, despite having indications for randomization, do not have the technical possibility of clipping during the intervention.

3.5. VARIABLES TO STUDY : The patients included in the study will have their pre-surgical hemoglobin determined by preoperative analysis and another post-surgical hemoglobin sample will be determined the day after surgery. The need for transfusion, blood loss during surgery (aspirate the blood content), surgical time, hospital stay, symptom improvement and complications will be assessed.

In addition, clinical data on the patients will be collected: age, height, weight, race, concomitant diseases and treatment, family history, age at menarche, tobacco and alcohol consumption, main clinic where the surgery is performed.

3.6. INFORMATION SOURCES :

To obtain the necessary information from the study, the HCIS medical records will be used.

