3.7. STATISTICAL ANALYSIS OF THE DATA

The data collected from the medical records will be tabulated in a main database with the SPSS version 23.0 program (IBM Corp. Released 2008. IBM SPSS Statistics for Windows, version 23.0 Armonk , NY: IBM Corp) For the statistical analysis, the same program will be used. The time for patient recruitment and data collection can be estimated at one year.

The absolute and relative frequency distributions of the qualitative variables will be presented.

The differences in the values of the quantitative variables will be studied using the most appropriate test in each case, Student 's t test to compare two groups and the corresponding non-parametric ones.

In the analysis of the contingency tables for qualitative variables and their possible association between them, Pearson's chi-square test will be used.

In all the analyzes the level of statistical significance is considered with a minimum probability of 95% ($p < 0.05$).

4 . ETHICAL AND LEGAL ASPECTS

The study will be governed by the basic ethical principles contained in the Declaration of Helsinki (*WORLD MEDICAL ASSOCIATION DECLARATION OF HELSINKI. Ethical principles For Medical Research Involving Human Subjects . Adopted by the 18th WMA General Assembly Helsinki, Finland , June 1964 and amended by the 29th WMA General Assembly , Tokyo , Japan , October 1975; 35th WMA General Assembly , Venice , Italy , October 1983; 41st WMA General Assembly , Hong Kong, September 1989; 48th WMA General Assembly , Somerset West, Republic of South Africa , October 1996 and; the 52nd WMA General Assembly , Edinburgh, Scotland, October 2000 and note of clarification on paragraph 29 added by the WMA General Assembly , Washington 2002 and its amendments of 2004, 2008 and 2013*), in the Guide to Good Clinical Practices in Human Health Research, in LAW 14/2007, of July 3, on Biomedical Research, published in BOE No. 159 of Wednesday, July 4, 2007, in the Agreement for the Protection of Human Rights and the Dignity of the Human Being with respect to the Applications of Biology and Medicine, drawn up in Oviedo on April 4, 1997 and signed on July 23, 1999, and accepted by the Biomedical Research Law 14/2007. In accordance with said agreement, the data obtained will never be used for profit (article 21) and may not be used for a purpose other than that for which it is reported in this document (article 22).

4.1. CONFIDENTIALITY OF THE DATA.

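### The main objective rests on two unranked measures, haemoglobin and aspirated volume, and the plan does not say which result decides the trial

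*Combined protocol and SAP*

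**What the plan says.** - **Section 2, main objective.** Efficacy is to be identified "by comparing blood loss (by assessing pre- and postoperative hemoglobin in g/dL and intraoperative blood aspirate in milliliters"). The two measures are listed together and neither is ranked.
- **Summary, main objective.** The aim is "to assess whether there are significant differences in terms of a decrease in intraoperative blood loss" between patients with and without clamping. No measure is named.
- **Summary, sample size.** With 37 patients per group, the calculation rests on "a difference in hemoglobin levels of 0.7 g/dl between the two groups, with a statistical power of 80% and an alpha error of 5" per cent. No effect in millilitres is given anywhere.
- **Section 3.5, repeated in 5.4.** Haemoglobin is measured before surgery, and "another post-surgical hemoglobin sample will be determined the day after surgery". Listed separately from it is "blood loss during surgery (aspirate the blood content"). Neither is called primary.
- **Section 3.7.** "In all the analyzes the level of statistical significance is considered with a minimum probability of 95" per cent (p < 0.05). Quantitative variables are compared by a t test or a non-parametric counterpart, chosen case by case. There is no testing order, adjustment or success rule.

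**The concern.** A trial with one main question needs one pre-stated result that answers it, or a rule for combining several. Here the documents point both ways. The sample-size statement points to haemoglobin. The Summary's objective is intraoperative blood loss, and Sections 3.5 and 5.4 use the corresponding term for the aspirate. Section 2 names both.

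If haemoglobin and aspirate disagree, the plan does not say whether the main objective was met, and the answer could be chosen once the results are known. The 5% and 80% in the Summary then cannot be read as properties of the trial's conclusion, because they belong to one of the two comparisons. The choice of test for haemoglobin is also left open, which adds a second decision that could be made after the data are seen.

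**Working it through.** **Inputs from the documents:** 37 per group, haemoglobin difference 0.7 g/dL, power 80%, alpha 5% (Summary); p < 0.05 for all analyses (Section 3.7). **Assumed:** two-sided tests, the correlation between the two test statistics (0 to 0.9), 80% power for aspirate, and the correlation between pre- and post-surgical haemoglobin.

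**1. The plan's own figure.** The documents give no SD, so 37 per group can only be solved backwards. With a two-sided 5% t test on 72 degrees of freedom, 80% power at 37 per group needs a standardised difference of 0.660. The implied SD is 0.7 / 0.660 = 1.06 g/dL. This SD is used in step 5.

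**2. If haemoglobin alone decides.** One test at 5%: the stated alpha and power can stand.

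**3. If either result counts.** With no effect on either measure, the false-positive chance is 1 − P(|Z1| < 1.96 and |Z2| < 1.96), with Z1 and Z2 bivariate normal. At correlation 0 this is 1 − 0.95² = 0.0975.

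**4. If both are required.** Joint success cannot be more probable than haemoglobin success alone. So the chance of wrongly claiming an effect on both is at most 5%, and power is at most 80%. If aspirate also had 80% power, each statistic would have mean 1.960 + 0.842 = 2.802, and joint power is P(Z1 > 1.96 and Z2 > 1.96). At correlation 0 this is 0.80 × 0.80 = 0.640.

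| Correlation | Either counts: false-positive chance | Both required: joint power |
|---|---|---|
| 0 | 9.75% | 64.0% |
| 0.3 | 9.5% | 66.6% |
| 0.5 | 9.1% | 68.7% |
| 0.7 | 8.3% | 71.3% |
| 0.9 | 7.0% | 75.0% |

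**5. ANCOVA on haemoglobin at 37 per arm.** Power comes from the noncentral t with 71 degrees of freedom, allowing for chance baseline imbalance. If 1.06 is the SD of the post-surgical level, the residual SD at pre/post correlation r is 1.06 × √(1 − r²).
- r = 0: residual SD 1.06, power 0.794.
- r = 0.5: residual SD 1.06 × √0.75 = 0.918, power 0.895 (0.8946 before rounding, so about 89%).

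If 1.06 is instead the SD of the change, the residual SD is 1.06 × √((1 + r)/2). This gives 0.895 at r = 0.5, 0.855 at r = 0.7 and 0.794 as r approaches 1. On either reading the worst case is about 79%.

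**6. Fixed order, haemoglobin then aspirate.** If haemoglobin has no true effect, any false claim must first pass its 5% test. If haemoglobin truly differs, the only possible false claim is on aspirate, also at 5%. The chance of any false claim therefore stays at about 5%.

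**The case against.** The strongest reply is that a trial sized on haemoglobin has haemoglobin as its primary outcome by implication, so nothing is inflated. The sizing is real evidence, but the documents never state the inference, and the Summary's objective together with the wording of Sections 3.5 and 5.4 supports aspirate at least as directly. The reply shows which choice is natural, not that it has been made.

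Two stronger readings are tempting and are not supported:
- A reader might infer that the trial runs at nearly 10% false positives. That needs an either-counts rule, which the documents do not state, and zero correlation between two measures of the same bleeding, which is the extreme case.
- A reader might take the conjunction in Section 2 to mean that both results must be significant. The phrase describes how blood loss is assessed; it is not a success rule.

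It is also fair to say that the t test in Section 3.7 is valid for a randomised comparison. ANCOVA is recommended because it fixes the analysis in advance and usually gains precision from a measurement already planned, not because the t test is wrong.

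**Conclusion.** The point holds as a missing primary outcome and a missing decision rule, and it should be fixed. It is not a demonstration that alpha is inflated. The effect is nil if haemoglobin alone decides. If either result suffices, the two-sided false-positive chance is 7.0% to 9.75%. If both are needed, alpha is kept but power is capped at 80% and is 64% to 75% when aspirate also has 80%.

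The correlations and the aspirate power are assumptions; actual power for aspirate cannot be computed, since no difference or SD in millilitres is given. The absence of a rule is judged on the text available for review, in which the statistical section is present; some pages had been removed.

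**What to change.** Before outcome data are examined, make these changes in the Summary, Section 2 and Section 3.7:

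1. Name one primary outcome. Haemoglobin is the natural choice because the stated sample size, power and alpha refer to it. If the sponsor prefers aspirated volume, the 80% no longer describes the primary outcome and the power statement must be redone for it.
2. With haemoglobin primary, replace the case-by-case test choice with the between-arm difference in day-after haemoglobin adjusted for pre-surgical haemoglobin (ANCOVA, two-sided 5%, 95% CI).
3. Make aspirated volume the first secondary outcome, with its test named in advance. Test it confirmatorily only if haemoglobin is significant; otherwise report it with its 95% CI.

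**Cost:** a few sentences and no new data, since both haemoglobin values and the aspirate are already planned. The sample size stays at 37 per arm. If the original calculation was two-sided, ANCOVA power is about 79% at worst and about 89% at an assumed pre/post correlation of 0.5; these figures do not carry over to a one-sided calculation. The real concession is that a significant aspirate result alone could no longer support the main claim.

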3. METHODOLOGY

3.1. DESIGN : Longitudinal prospective randomized clinical trial.

3.2. SUBJECTS OF STUDY : Patients with symptomatic fibroids who require surgery to treat them, from the Gynecology Service of the Ramón y Cajal Hospital. Patients will be randomized into 2 groups: exposed (patients with temporary occlusion of the uterine arteries by clips during surgery) and non-exposed (patients without temporary occlusion of the uterine arteries during surgery).

A patient will be recruited in the pre-surgical consultation when laparoscopic myomectomy is indicated, randomizing both groups by simple random sampling. An informed consent will be delivered to the patients, who have to accept and sign in order to participate in the study. The diagnosis of the presence of fibroids will be made by abdominal and/or transvaginal gynecological ultrasound and/or nuclear magnetic resonance. Fibroids will be quantified, measured and their location described.

3.3. INCLUSION CRITERIA : The inclusion criteria to participate in the study are the existence of uterine fibroids with an indication for laparoscopic surgery and the patient's desire to preserve the uterus.

3.4. EXCLUSION CRITERIA : Patients who do not meet the inclusion criteria, women with symptomatic fibroids who are not candidates for laparoscopic surgery and/or do not

wish to preserve the uterus, those patients who, despite having indications for randomization, do not have the technical possibility of clipping during the intervention.

3.5. VARIABLES TO STUDY : The patients included in the study will have their pre-surgical hemoglobin determined by preoperative analysis and another post-surgical hemoglobin sample will be determined the day after surgery. The need for transfusion, blood loss during surgery (aspirate the blood content), surgical time, hospital stay, symptom improvement and complications will be assessed.

In addition, clinical data on the patients will be collected: age, height, weight, race, concomitant diseases and treatment, family history, age at menarche, tobacco and alcohol consumption, main clinic where the surgery is performed.

3.6. INFORMATION SOURCES :

To obtain the necessary information from the study, the HCIS medical records will be used.

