- 5.2. Patient recruitment:** Patients will be recruited in the pre-surgical consultation, when laparoscopic myomectomy is indicated, randomizing both groups by simple random sampling. An informed consent will be delivered to the patients, who have to accept and sign in order to participate in the study. Fibroids will be quantified, measured and their location described.
- 5.3. Performing the surgical act:** during the laparoscopic myomectomy, temporary occlusion of the uterine arteries will be carried out using clips in those patients who are assigned to the exposed group.
- 5.4. Data collection: the pre-surgical hemoglobin determination** will be collected through the preoperative analysis and another post-surgical hemoglobin sample will be determined the day after surgery. The need for transfusion, blood loss during surgery (aspirate the blood content), surgical time, hospital stay, symptom improvement and complications will be assessed ; in addition to clinical data of the patients.
- 5.5. Statistical analysis of the collected data.**

6. BIBLIOGRAPHICAL REFERENCES:

3: Bedaiwy MA. Uterine artery occlusion at myomectomy? Towards a better definition of the indications. *Fertile Sterile* . 2019 Apr;111(4):685-686. doi : 10.1016/j.fertnstert.2019.01.024. Epub 2019 Mar 8. PubMed PMID: 30853090.

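### The plan never says that patients are analysed in their assigned arm, and its wording by procedure received would let a control patient occluded for bleeding change group or drop out

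*Combined protocol and SAP*

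**What the plan says.** Allocation comes first. Sections 3.2 and 5.2 place randomisation at the pre-surgical consultation, and 3.2 states: "Patients will be randomized into 2 groups: exposed (patients with temporary occlusion of the uterine arteries by clips during surgery". The other arm is described as "non-exposed (patients without temporary occlusion of the uterine arteries during surgery". Section 5.3 has the clips applied "in those patients who are assigned to the exposed group".

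The analysed groups are described differently. The Summary's main objective begins "To analyze the patients who underwent a laparoscopic myomectomy". Its study population paragraph reads "A total of 37 patients who underwent laparoscopic myomectomy with temporary occlusion of the uterine arteries and utero-ovarian ligaments using clips will be analyzed", set against a "control group of 37 patients who underwent laparoscopic myomectomy with the traditional technique". That is the only place where the plan says who is analysed in each group.

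Section 3.7 names the tests (Student's t test, its non-parametric counterparts and Pearson's chi-square) but no analysis population. Section 3.4 excludes women who "do not have the technical possibility of clipping during the intervention", which can be known only after randomisation. Sections 3.5 and 5.4 list transfusion, aspirated blood loss, surgical time, hospital stay, symptom improvement and complications. They do not list occlusion used in a control patient, conversion to laparotomy or hysterectomy. Nothing in the documents mentions any of those three events or how such a patient would be classified.

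**The concern.** In a randomised comparison, group membership should be fixed at allocation. Here the words that say who is analysed depend on the operation performed, and the operation can change because of the outcome. The surgeon necessarily knows whether clips were applied. If clips are placed in a control patient to control bleeding, she no longer fits the non-exposed description and does fit the exposed one. If a patient is converted, she may no longer count as having undergone laparoscopic myomectomy in the Summary's sense.

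The patients affected would be those with the heaviest bleeding. Removing them from the control arm makes that arm look better than it is. Adding them to the occlusion arm also charges their blood loss, transfusions and complications to the technique under test. With 37 patients per arm, one or two such cases are enough to matter.

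**Working it through.** **1. The passages side by side.**

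| Place | Group defined by |
|---|---|
| 3.2, main clause | randomisation |
| 5.3 | assignment (who receives clips) |
| 3.2, glosses in brackets | occlusion present or absent during surgery |
| Summary, who is analysed | technique undergone |
| 3.4, last exclusion | an intraoperative finding |
| 3.7 | nothing stated |

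The first two lines settle how the arms are created and who is to be clipped. Neither settles where a patient is counted if the operation departs from the allocation.

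**2. The plan's own figure.** The Summary gives 37 per group for a 0.7 g/dL hemoglobin difference, 80% power and 5% alpha, without a standard deviation (SD) or sidedness. The two-sided SD that yields 37 is

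SD = 0.7 × √(37/2) / (1.960 + 0.842) = 0.7 × 4.301 / 2.802 = 1.07 g/dL.

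This value is back-solved, so it is an assumption. The figure of 37 is not in dispute.

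**3. Shift in the observed difference.** Set the mean hemoglobin fall to 0 in the 37 assigned controls and to −0.7 in the 37 assigned to occlusion. Let k controls have a fall x g/dL above the control mean. The remaining controls then average −kx/(37 − k).

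- Dropped: 0.7 − kx/(37 − k)
- Counted as exposed: −kx/(37 − k) − [37 × (−0.7) + kx]/(37 + k)

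For k = 2 and x = 3:

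- Dropped: 0.7 − 6/35 = 0.53
- Counted as exposed: −6/35 + 19.9/39 = −0.171 + 0.510 = 0.34

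| k of 37 | x (g/dL) | Dropped | Counted as exposed |
|---|---|---|---|
| 1 | 2 | 0.64 | 0.57 |
| 2 | 2 | 0.59 | 0.45 |
| 3 | 2 | 0.52 | 0.32 |
| 1 | 3 | 0.62 | 0.52 |
| 2 | 3 | 0.53 | 0.34 |
| 3 | 3 | 0.44 | 0.16 |

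Both k and x are assumptions; the documents give neither.

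**4. A check that does not choose x.** In 20,000 simulated trials (normal falls, SD 1.07, true difference 0.7, 37 per arm), the k worst control bleeders were moved or dropped. Their outcomes were left as observed.

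| k | As assigned: difference (power) | Dropped | Counted as exposed |
|---|---|---|---|
| 1 | 0.70 (79%) | 0.64 (73%) | 0.56 (59%) |
| 2 | 0.70 (79%) | 0.58 (66%) | 0.44 (38%) |
| 4 | 0.70 (79%) | 0.49 (52%) | 0.24 (12%) |

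With no true difference, counting the worst two as exposed gives −0.22 on average. The two-sided test then rejects in about 14% of trials instead of 5%, almost always against occlusion.

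**The case against.** The strongest reply is that the arms are randomised arms. The 3.2 sentence opens with randomisation, the brackets can be read as what each group is meant to receive, and 5.3 uses exposed as a label for assignment. The Summary's past tense may be loose phrasing. This stands to the following extent: a reader might infer that the plan defines its arms by treatment received, or that rescued controls will be reclassified and the worst bleeding hidden. The documents do not support that. They do not mention rescue occlusion or conversion at all, so reclassification is something the text permits, not a rule it lays down.

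The conversion limb is the weaker one. A control patient converted to laparotomy still had no occlusion and still fits the non-exposed description. The candidacy and uterus-preservation criteria in 3.3 and 3.4 concern eligibility, not events in theatre. Only the Summary's wording would remove her. Conversion could also occur in either arm, so a bias against occlusion from that source assumes it is commoner in controls. Rescue with something other than temporary clip occlusion would not meet the exposed description either.

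The inputs can be called severe. At SD 1.07, a 3 g/dL excess is 2.8 SD, and under normality about 0.09 of 37 controls would exceed it. A 2 g/dL excess is 1.87 SD, which about 1.1 of 37 would exceed (37 × 0.031). Hemoglobin is measured the day after surgery, so transfusion could shrink the recorded excess. These points argue for the milder end of the range; they do not change the direction.

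Conversion and hysterectomy might be captured under complications, but the plan does not define that term.

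**Conclusion.** The point holds as an omission combined with wording that points the wrong way. The one sentence on who is analysed selects by technique undergone, 3.2 glosses the arms likewise, 3.4 already removes patients for an intraoperative finding, and 3.7 contains nothing to override this. Following the text literally could move or drop a control patient because of the primary outcome, with bias against occlusion.

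The size is unknown because no crossover rate is given. For 1 to 3 of 37 controls with a 2 to 3 g/dL excess fall, a true 0.7 g/dL would appear as 0.64 to 0.44 if they are dropped, and as 0.57 to 0.16 if they are counted as exposed. This assumes that the extra occlusion did not itself alter the recorded fall.

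The clip-not-possible exclusion in 3.4 is a related but separate route. Deleting that clause alone would leave this one open, whereas a clear rule to analyse by assigned arm would deal with both.

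**What to change.** - **Summary and 3.2:** define the groups as assigned to temporary occlusion and assigned to no occlusion.
- **3.7:** state that the primary analysis includes every randomised patient who is operated on, in the assigned arm, whatever procedure was done. Report by arm the number randomised but not operated on. Label any as-treated analysis as secondary. Bring the intraoperative exclusion in 3.4 into line with this rule.
- **3.5 and 5.4:** record occlusion used in a control patient, conversion to laparotomy, and hysterectomy, each with its reason, and report them by assigned arm.

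The cost is a few sentences and three fields that can be taken from the operative note. The stated 37 per group is unchanged. The one small downside is that rescue occlusion in controls slightly dilutes the contrast between arms. The change sets how patients are counted; it does not touch clinical management.

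### Fibroid burden is measured before surgery but used in neither allocation nor analysis; put one burden measure in the primary haemoglobin model

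*Combined protocol and SAP*

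**What the plan says.** The Summary plans "A total of 37 patients who underwent laparoscopic myomectomy with temporary occlusion" and compares them "with a control group of 37 patients who underwent laparoscopic myomectomy with the traditional technique", which makes 74 in total. The size is justified by the statement that "there is a difference in hemoglobin levels of 0.7 g/dl between the two groups", with 80% power and 5% alpha. No standard deviation is given.

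Sections 3.2 and 5.2 both recruit at the pre-surgical consultation, "randomizing both groups by simple random sampling". Both also say that the fibroids will be counted, measured and located. The text available for review describes no blocks, strata, method of generating the sequence or concealment of it, and no rule for holding each arm at 37. Section 5.1 says only that recruitment continues until the planned size is reached.

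Section 3.7 compares quantitative variables between groups with Student's t test or a non-parametric counterpart. It names no covariate. The main objective in section 2 is blood loss, assessed by haemoglobin before and after surgery and by aspirated volume. The sample size rests on haemoglobin.

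**The concern.** The introduction says that surgical planning for myomectomy should rest on the location, size and number of fibroids, and it names bleeding as one of the most frequent complications. It is a modest inference that burden predicts blood loss. The protocol does not state it or quantify it.

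If burden does predict blood loss, two things follow in a trial of this size. First, a noticeable difference in burden between the arms can arise by chance, and the plan has no prespecified way to allow for it. An adjustment chosen after seeing the baseline table would be open to challenge. Second, even when the arms are balanced, the variation in blood loss due to burden stays in the error term of the t test, so the trial gives up precision that data it already collects could supply.

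**Working it through.** **Inputs.** From the Summary: 37 per arm, difference Δ = 0.7 g/dL, power 80%, alpha 5%. Assumed: two-sided test; burden factor prevalence 30–50%; share of outcome variance explained by burden (R²) 10–20%. Back-solved: the SD.

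**1. The plan's own figure.** With the normal approximation, n per arm = 2(1.960 + 0.842)²σ²/Δ² = 15.70σ²/0.49. This gives 37 when σ is about 1.061–1.074 g/dL; for example, σ = 1.07 gives 36.7, rounded up to 37. The noncentral t distribution gives exactly 80% at 37 per arm with σ = 1.06. Since no SD is stated, 37 can be shown to be attainable but cannot be confirmed: σ = 0.8 would need 21 per arm and σ = 1.5 would need 73. A one-sided test would imply σ of about 1.20–1.21.

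**2. Chance imbalance in burden.** For a binary factor with prevalence p, the difference between arms has SE = √[p(1−p) × 2/37].

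| p (assumed) | SE | 0.20/SE | P(difference ≥ 20 points), normal | Same, simulated under simple allocation |
|---|---|---|---|---|
| 0.30 | 0.107 | 1.88 | 6.0% | 6.0% |
| 0.50 | 0.116 | 1.72 | 8.5% | 8.9% |

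For a continuous measure, the standardised difference has SE √(2/37) = 0.23, so it exceeds 0.3 SD in about 20% of trials.

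Unstratified permuted blocks barely change this. The simulated chance of a difference of 20 points or more is 5.8–6.0% at p = 0.30 and 8.1–8.2% at p = 0.50. Blocks stratified on the factor bring it to about 0%.

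**3. What adjustment gains.** Noncentrality λ = Δ / [σ√(1−R²) × √(2/37)], with √(2/37) = 0.2325 and 72 degrees of freedom (71 with the covariate).

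| R² (assumed) | Residual SD, g/dL | λ | Power |
|---|---|---|---|
| 0 (plan's t test) | 1.060 | 2.84 | 80.0% |
| 0.10 | 1.006 | 2.99 | 84.0% |
| 0.20 | 0.948 | 3.17 | 87.9% |

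If the covariate explains nothing, only one degree of freedom is lost, and power stays at 80.0% to one decimal. The gain is similar at other SDs. At σ = 1.0 power goes from 84.4% to 87.9–91.3%, and at σ = 1.2 from 69.7% to 74.2–79.0%.

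**4. Arm sizes under simple randomisation.** With Binomial(74, 0.5), P(37/37) = C(74,37)/2⁷⁴ = 9.2%. The SD of an arm's count is √(74 × 0.25) = 4.3, and the central 95% range is 29–45. A split of 32/42 or worse occurs in 29.5% of trials. At σ = 1.06, power is 79.3% at 32/42 and 77.6% at 28/46. Averaged over all splits it is 79.5%, a loss of 0.5 points.

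**The case against.** Simple randomisation is a valid method. It supports an unbiased comparison and a correct type I error, unequal arms do not bias a t test, and the power cost is trivial. All of that stands. A reader might still infer three stronger claims that the documents do not support.

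- **That imbalance in burden would confound the result.** Chance imbalance under valid randomisation costs precision and credibility in the one trial that is run. It is not a systematic bias.
- **That the last allocations will be predictable because an arm closes at 37.** About 7 of the 74 assignments would be predetermined on average under such a rule, but no section states one. The wording "randomizing both groups by simple random sampling" could even mean drawing 37 positions from a list of 74, which would give 37/37 exactly. Sequential recruitment at the consultation makes independent allocation the more natural reading, but the text does not settle it.
- **That permuted blocks would repair both arm size and burden at no cost.** Unstratified blocks leave burden where it was. In an open single-centre trial they are also easier to guess. Simulating a recruiter who always bets on the arm that is behind gives about 14 excess correct guesses out of 74 with varying blocks of 4 and 6. Simple allocation gives 0, and closing an arm at 37 gives 3.4. Varying and hiding the block size does not defeat that strategy.

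Two further limits apply. Pages were removed from the text available for review, so the absence of concealment means only that it is not described there. Nor does any allocation scheme protect the analysed numbers from the exclusion in 3.4 of patients found at surgery to be unsuitable for clipping. That is a separate matter.

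**Conclusion.** The point holds as a missed gain in the analysis, not as a flaw in the validity of the randomisation. Burden is recorded before surgery and then used nowhere in the comparison. At an assumed prevalence of 30–50%, a difference of 20 points or more between the arms would occur in about 6–9% of trials. Using burden as a covariate would raise power from 80% to about 84–88% if it explains an assumed 10–20% of outcome variance, and would cost essentially nothing if it explains none. These power figures rest on a two-sided test and an SD of about 1.06 g/dL, back-solved from 37 per arm.

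The mismatch between 37 per arm and simple randomisation is real but minor. Exact equality occurs in about 9% of trials, at an average cost of about 0.5 power points.

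**What to change.** **Main change, in 3.7.** Before enrolment, prespecify a linear model for the primary haemoglobin outcome with terms for treatment group and one named preoperative burden measure, for example largest fibroid diameter. Use it in place of the unadjusted t test. The cost is a sentence or two and one degree of freedom; the data are already collected and the planned software can fit the model.

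**Optional, in 3.2 and 5.2.** Stratify allocation by the same factor, using blocks of randomly varying size from a list concealed until after consent, and keep the factor in the model. This needs a prepared list and a stratum look-up at allocation. The protocol should name the downside: blocks make upcoming assignments more guessable in an open single-centre trial. If that is not acceptable, keep simple randomisation and rely on the adjusted model.

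**Clarification, in the Summary, 3.2 and 5.2.** Say how the sequence is generated and concealed, and describe 37 per arm as approximate unless the allocation method enforces it.
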